1) **Protocol Title**

Antipruritic effect of topical ketamine, amitriptyline, and lidocaine

2) **IRB Review History***

N/A

3) **Objectives***

The purpose of this study is to examine the antipruritic efficacy of topical ketamine, amitriptyline, lidocaine, and a tri-combination of ketamine, amitriptyline and lidocaine (hereafter referred to as “KeAmLi”) using non-histaminergic itch provocations in healthy volunteers. The primary outcome is itch reduction (AUC) between the vehicle and active treatment (KeAmLi-combo). Secondary outcomes include modality-specific analgesic properties of the topically applied ketamine, amitriptyline, lidocaine, and KeAmLi-combo to controlled quantitative thermal and mechanical stimuli, which can improve our understanding of the mechanism of action of these substances in the context of topical therapy.

4) **Background***

Introduction

Chronic itch is a prominent symptom of many dermatological conditions such as atopic dermatitis (AD), urticaria, psoriasis and prurigo nodularis, as well as neuropathic itch conditions. Moreover, itch is also common in conditions such as biliary cirrhosis, renal deficiency as well as several infectious-, allergic-, neoplastic-, autoimmune-, and drug-induced conditions¹⁻³. Itch almost inevitably leads to scratching of the affected area which can further exacerbate the skin inflammation and deterioration, leading to a vicious “itch-scratch cycle”^{4,5} characterized by maintenance of skin aberrations, cutaneous infections and pain^{5,6}. According to recent epidemiological studies, AD alone affects 5-20% of children worldwide with an estimated direct annual cost of nearly \$3 billion in the USA alone⁷. Itch is usually the primary complaint of these patients and has been reported to occur in as much as 87% of adult AD patients⁸. The currently available treatment options are suboptimal for most chronic itch conditions^{3,9}.

Rational for investigation of compounds for topical application

Ketamine is a potent N-Methyl-D-aspartate receptor (NMDAR) antagonist and a weak activator of μ -opioid receptors. Apart from being

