- 5) Currently enrolled in any investigational study in which the subject is receiving any type of drug, biological, or non-drug therapy.
- 6) Use of oral, topical analgesics, or other medications known to interfere with itch or pain perception 48 hours prior to the study visits (e.g. antihistamines, anesthetics, anti-inflammatories, opioids, neuroleptics, etc.).

- 7) Use of emollients on the volar aspects of the forearms arms on the day of the study visit.
- 8) Use of anti-depressants, anti-psychotics, and illicit drugs.
- 9) Known history of neuropathy, uremia, uncontrolled thyroid disease, and diabetes mellitus.
- 10) Known history of anaphylactic shock, or allergy to cowhage and/or known adverse reactions to lidocaine (or other local anesthetics of the amide type), ketamine or amitriptyline.
- 11) Pregnant (females of childbearing potential will undergo an hCG pregnancy test).
- 12) Currently incarcerated.

6) Number of Subjects*

A priori power calculations were conducted in G*Power based on data from a previous test-retest study³⁸. In order to have an effect 80% power with a size effect of 0.30 and alpha error probability of 0.05, we will need 36 subjects (10 within post hoc pairwise comparisons). We estimate that we will need to screen up to 42 individuals in order to enroll 36 healthy subjects.

We will seek to recruit a sample with an approximately equal gender distribution.

7) Study-Wide Recruitment Methods*

IRB approved flyers will also be placed around the University of Miami medical campus, and within the waiting rooms of the Department of Dermatology Out Patient Clinic at UMH (South Building, suites K-M) and at the Lennar Foundation Medical Center.

8) Study Timelines*

This projected is expected to last 8 months. The first 6 months will be dedicated to subject enrollment. During this time each subject will be a part of 2 study visits; one session lasting approximately 2.75 hours and one lasting approximately 2 hours. The second session must be completed within 7 days of the first session. The second 2 months will be dedicated to the sample analysis and the last month will be dedicated to dissemination of findings.

9) **Study Endpoints***

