The primary endpoints are visual analog scale (VAS) ratings of the perceived intensity of itch sensation elicited by epicutaneous application of cowhage spicules (non-histaminergic itch) on the volar aspects of the forearms comparing skin pretreated with vehicle cream with the KeAmLi-combination. Ratings will be plotted vs. time to generate a temporal itch intensity graph and the area under the curve (AUC) will be calculated for each subject. The secondary study endpoints are the individual itch peak intensity, itch peak time, and itch time duration comparing skin pretreated with vehicle cream with ketamine, amitriptyline, lidocaine, and KeAmLi-combination.

The exploratory outcomes (for all experimental interventions vs. the vehicle condition) are:

- Warmth detection threshold (°C needed to perceive warmth sensation)
- Heat pain threshold (°C needed to perceive heat pain)
- Mechanical detection threshold (mN needed to perceive touch)
- Mechanical pain threshold (mN needed to perceive pain)
- Development of hyperknesis (NRS ratings of itch evoked by touch before vs. after cowhage provocation)

10) **Procedures Involved***

At the beginning of the first session, subjects will be asked to fill out an informed consent, and a form for demographic information including health information. They will also be asked if they have taken any allergy or pain medicine during the past 24 hours. If so they will be asked to come back at a later time since these drugs might interfere with the study. Females of childbearing potential will undergo an hCG pregnancy test. Finally, subjects will receive instruction on the use of the visual analog scale for rating the intensity of itch sensation. Below is a short procedural overview of the proposed study this is followed by sections introducing in details each of the methods applied.

Subjects will be seated comfortably in a chair with both arms resting on armrests or on a pillow. Using a block-randomized design, we will deliver either topical vehicle (PCCA Lipoderm[®]), topical ketamine 10%, topical amitriptyline 5%, lidocaine 5% or KeAmLi-combo (ketamine 10%, amitriptyline 5%, and lidocaine 5%) to four 4 x 4 cm predefined skin areas on the ventral forearms over two study visits. The 1st visit will involve applying 3 of the 5 treatments (randomized), to 3 of the 4 designated test sites in a randomized manner. The 2nd visit will involve applying the

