Statistical Analysis: Data will be entered into a database program, such as Microsoft Excel and/or IBM SPSS, and analyzed at using Prism GraphPad 6 and/or IBM SPSS. Basic descriptive statistics using mean (SEM), range, and n (%) will be calculated in Excel and presented. Statistical significance will be set at $p < 0.05$. Analysis will be performed within and between groups.

Normality assessment will be tested by visual inspection and Shapiro-Wilks tests. A repeated measure (between–within) ANOVA will be used for the main analysis and post hoc comparisons will be conducted using the Bonferroni correction in a manner similar to Dunnett’s test.

Blinding procedures: The study will be conducted under double-blinded conditions. The investigators responsible for the data collection, i.e. application, sensory tests, itch provocations, and data entry, will be blinded to the substance being applied. Blinding will be carried out by random allocation of letters “A” to “E” to labels on the pharmaceuticals (including the vehicle). This task is carried out at the compounding pharmacy. With delivery of the pharmaceuticals a list specifying the compounds corresponding to allocated letters is supplied to the PI. In case of serious adverse effects, the PI will breach the blinding. Otherwise unblinding will not occur until after the primary analysis has been conducted.

Local safety assessment: After pretreatment with each ointment (before any sensory testing is performed), and after each cowhage application a local safety assessment will be done. Erythema, edema, and any other local reaction will be recorded on a 5-point Likert scale (0=clear, 1=almost clear, 2=mild, 3=moderate, 4=severe).

11) **Data Management***

All of the data, including records of subjects, source documents, and informed consent will be kept in the study center office under lock for 6 years after the study finished. The study center office is located at: [name].

12) **Provisions to Monitor the Data to Ensure the Safety of Subjects***

The study team will be responsible for protecting the safety, rights, and well-being of study participants. When testing is performed the subjects' vital signs (blood pressure, heart rate, and respiratory rate) will be monitored.

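### The single primary contrast, itch AUC for KeAmLi against vehicle, is tested only as a Bonferroni-corrected post hoc comparison, which gives up power that the trial need not lose

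*Combined protocol and SAP*

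**What the plan says.** Section 3 (Objectives) reads: "The primary outcome is itch reduction (AUC) between the vehicle and active treatment (KeAmLi-combo". Section 9 (Study Endpoints) repeats this for the VAS itch ratings and their AUC, "comparing skin pretreated with vehicle cream with the KeAmLi-combination". The single agents enter only below that level. The secondary itch endpoints are assessed "comparing skin pretreated with vehicle cream with ketamine, amitriptyline, lidocaine, and KeAmLi-combination", and the exploratory outcomes are set out "for all experimental interventions vs. the vehicle condition".

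The Statistical Analysis paragraph in section 10 gives a general significance level of 0.05. It then says of a repeated-measures ANOVA that it "will be used for the main analysis and post hoc comparisons will be conducted using the Bonferroni correction in a manner similar to" a named method, Dunnett's test. No separate test, alpha, testing order or exemption is given for KeAmLi against vehicle, and the size of the Bonferroni family is not written.

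Section 6 (Number of Subjects) has one power statement: 80% power, an effect size of 0.30, "alpha error probability of 0.05, we will need 36 subjects (10 within post hoc pairwise comparisons". It names neither the test nor the effect-size metric. The 10 may count subjects or pairs.

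**The concern.** The omnibus F test covers five conditions, so it does not answer a question about two of them. The stated route to the primary question is therefore the corrected post hoc comparison. Bonferroni protects a family of comparisons of equal standing. Here one comparison was singled out in advance and the others were ranked below it, so dividing its alpha buys no protection that the primary claim needs.

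At stake is a primary result that is significant at 0.05 but is reported as negative because of comparisons the protocol itself calls secondary. Because the divisor is not written, the choice between 1, 4 and 10 is also open when the data are analysed.

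**Working it through.** **Inputs.** n = 36 completers (section 6, and the stopping statement in section 12). Five within-subject conditions (section 10). Overall alpha 0.05 (section 6 and Statistical Analysis). Candidate divisors: 1 (primary contrast alone), 4 (each active against vehicle) and 10 = 5×4/2 (all pairs), giving alpha 0.05, 0.0125 and 0.005. The paired SD of AUC is not given. Differences are therefore expressed as d, the mean within-subject AUC difference divided by the SD of those differences. The two-sided paired t test (35 df) is my assumption for the contrast.

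**1. The plan's own figure of 36.** Several sets of G*Power inputs give 36 as the smallest N for 0.30, 80% and 0.05.
- Five conditions, one group, sphericity, f of the partial-eta-squared type: λ = f²(N−1)(m−1) = 0.09×35×4 = 12.6. Power is 80.9% at 36 and 79.6% at 35.
- Default f, λ = f²·N·m·ε/(1−ρ), five conditions, ρ = 0, ε = 0.7: λ = 0.09×36×5×0.7 = 11.34. Power is 81.0% at 36 and 79.7% at 35.
- Default f with two conditions and ρ of 0.22 to 0.24. At ρ = 0.22, λ = 0.09×36×2/0.78 = 8.31 and power is 80.0%. This is one pairwise contrast at 0.05, with d = √(8.31/36) = 0.48.

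The first two are omnibus calculations and the third is pairwise. The documents do not say which was used.

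**2. Results at n = 36, with no assumption about the 0.30.** The smallest significant observed d is t(1−α/2; 35)/√36. The d detectable with 80% power solves P(t′ > t_crit) = 0.80, with t′ noncentral t on 35 df and noncentrality 6d.

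| Divisor | Alpha | Critical t | Smallest significant observed d | d for 80% power | Power at d = 0.48 |
|---|---|---|---|---|---|
| 1 | 0.05 | 2.030 | 0.338 | 0.48 | 80% |
| 4 | 0.0125 | 2.633 | 0.439 | 0.58 | 60% |
| 10 | 0.005 | 2.996 | 0.499 | 0.64 | 46% |

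At a true d of 0.48, restoring 80% power would take 52 completers with a divisor of 4, or 62 with a divisor of 10. The last row applies only if the 10 in section 6 counts pairs.

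**3. The band where the verdict changes.** An observed d of about 0.34 to 0.44 is significant at 0.05 but not at 0.0125. With the pooled ANOVA error (35×4 = 140 df) the limits are 1.977/6 = 0.33 and 2.530/6 = 0.42, so the band does not hinge on the paired t test.

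**4. If the 10 counts subjects.** For 80% power, 10 subjects need d = 1.00 at 0.05 or 1.28 at 0.0125. At d = 1.0, 36 completers have 99.9% power at 0.0125 and 99.8% at 0.005, so the correction then costs almost nothing.

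**The case against.** The strongest reply is that Bonferroni over comparisons with a common control is valid and conservative, so this is a matter of efficiency. That stands: false positives are not inflated, and anyone who infers inflation from the missing family size is mistaken. But efficiency on the only primary question matters, and here it can be recovered at almost no cost. Using a true Dunnett critical value would not remove the loss. Its per-comparison level is about 0.0145 (normal approximation), which gains only about 2 points of power over a divisor of 4.

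A second reply is that section 6 may contain a pairwise power statement, since the 10 follows the word for subjects. This also stands. On that reading the planning difference is near 1.0 and the loss is negligible. It follows that a power loss of a definite size is not established.

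Three stronger readings are tempting but not supported:
- A reader might infer that the stated 80% belongs to the omnibus test and that the primary contrast was never powered. Step 1 shows that 36 also arises from a single pairwise contrast.
- A reader might take the post hoc tests to be allowed only after a significant F. The documents do not say so.
- A reader might infer that the blinding rule makes the primary test impossible, because "Otherwise unblinding will not occur until after the primary analysis has been conducted". It does not. The ANOVA and all ten pairwise tests can be run on letters A to E, and the relevant pair identified at unblinding.

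**Conclusion.** The point holds as a loss of power and a gap in specification. One contrast is named as primary, yet the only stated test that isolates it carries a correction it does not need, over a family of unstated size. On the likely reading of four comparisons, the difference detectable with 80% power rises by about a fifth (0.58/0.48 = 1.21), and power at a true d of 0.48 drops by 20 points. If the family is all ten pairs, the drop is 34 points.

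These figures assume 36 completers and a two-sided paired t test; they do not depend on what the 0.30 means. Whether the loss matters in practice depends on the true paired difference, which the documents do not allow anyone to judge: substantial near 0.5, negligible near 1.0. Which test the stated 80% power refers to cannot be determined. The change should be made because it is nearly free, not because the trial is shown to be underpowered.

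**What to change.** 1. In the Statistical Analysis paragraph, make KeAmLi against vehicle on itch AUC the single primary test: a within-subject contrast at two-sided 0.05, with no Bonferroni divisor and not conditional on the omnibus F. Treat the three single agents against vehicle as secondary, with one named correction, for example Holm over three comparisons.
2. In section 6, keep 36 subjects. Name the test and the effect-size metric behind the 0.30, and say whether the 10 counts subjects or pairs. Add that 36 completers give 80% power for a standardised paired difference of 0.48 in the primary contrast at two-sided 0.05.
3. Optionally, state that the primary contrast is run by a pre-written script on locked, coded data and identified at unblinding.

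The cost is protocol wording, with no change in sample size or procedures. The small downside is that familywise error is then controlled for the secondary comparisons separately from the primary one, rather than across all four together.

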remaining 2 treatments to 2 of the 4 designated test sites in a randomized manner. The subject and investigator will be blinded to the identities of the treatments (see blinding procedure below).

Application will be conducted with the investigator wearing nitrile gloves. The pre-treatment will occur under topical occlusion for 30 minutes to allow the ointment to be adsorbed. Following this, residual ointment will be removed and sensory testing, strictly within the pretreated area, will commence. For each of the five tested topical solutions the following procedures will be conducted (see also Fig. 1):

- 1) Demarcation of 4 x 4 cm treatment area (see Fig. 2)
 - a) Application of 2 g of ointment (randomized substance)
 - i) 30 min pretreatment
 - (1) During this time a subject familiarization procedure for the quantitative sensory testing will be conducted
 - ii) Removal of residual ointment
 - iii) Local safety assessment
- 2) Thermal sensory thresholds
 - a) HDT
 - b) HPT
- 3) Mechanical sensory thresholds
 - a) MDT
 - b) MPT
- 4) Baseline sensitivity to touch-evoked itch (STI) assessment
- 5) Cowhage provocation
 - a) 40-45 spicules rubbed into the epidermis
 - b) Continuous VAS-recording of itch and pain for up to 15 minutes
- 6) Post-provocation STI assessment (assessment of hyperknesis)
 - a) Spicules gently removed by 2-3 tape-strippings
 - i) 0
- 7) Procedure is repeated with next topical intervention

The second session is conducted in a manner completely identical to session 1. However, the remaining 2 ointments not used in session 1 are assessed in the second session. The second session must be completed within 7 days of the first session.

[figure not shown]

Figure 1 – Overview of the course of study procedures. Grey boxes in the top designate inclusion of subjects for sensory and skin parameters assessment in the depicted test-battery below. Thermal and mechanical sensitivity quantitative sensory tests are performed first, then assessment of STI is assessed and the itch provocation is conducted. Times estimates are derived from the DFNS protocol³⁹ and may vary between subjects mainly due to differences in the ease of understanding instructions. Abbreviations: WDT = warmth detection threshold; HPT = heat pain threshold; MDT = mechanical detection threshold, MPT = mechanical pain threshold; NRS = numeric rating scale; STI = Sensitivity to Touch-evoked Itch; VAS = visual analog scale;

[figure not shown]

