- c. **Lidocaine.** In the present study topical lidocaine 5% is applied. Lidocaine is an extremely well-studied and generally safe local anesthetic available for OTC use^{26,48,52-54}. Common side effects include local blanching and erythema. Contact hypersensitivity to lidocaine is rare but has been described^{52,54}. Systemic allergic (anaphylactic) reactions to lidocaine are exceedingly rare, particularly in response to percutaneous application^{52,55,56}. A systematic review on the use of ointment containing lidocaine found single dose percutaneous administration to be safe in neonates⁵³. In the present study lidocaine alone and in combination with amitriptyline and ketamine will only be applied in adults and to a relatively small area (4 x 4 cm) and as such the systemic exposure is negligible.

In the previous studies applying combinational use of above-mentioned substances no tendencies towards more frequent or more severe side effects have been reported.

15) Potential Benefits to Subjects*

There is no direct benefit to the subjects.

16) Vulnerable Populations*

No vulnerable populations will be enrolled in this study.

17) Sharing of Results with Subjects*

Results of this study will not be shared with the subjects, unless through scientific publication.

18) Setting

Potential subjects will be identified and recruited through IRB approved flyers.

Research procedures will be performed at the Miami Itch Center at the Lennar Foundation Medical Center or at the Department of Dermatology Research Clinic at UMH (West Building, rooms 504, 505, 506, &508).

19) Resources Available

The Principal Investigator [name], is a Professor from the Department of Dermatology & Cutaneous Surgery at the University of Miami. [name] primary research interest is in pruritus (itch) and the neurophysiology and innervation of skin in chronic itch. [name] has conducted research in the field of skin physiology, pharmacology, and neurophysiology of itch over the past 20 years. His research activities have centered on basic and clinical studies on itch neurophysiology and on clinical topics in dermatology, including topical and systemic formulations of anti-pruritics and skin barrier function and in itch in atopic eczema and psoriasis. [name] will assist with recruitment, study procedures, and assess adverse events.

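### The A–E code list goes to the PI at delivery with no protected custody, and coding is by product, so one break reveals every subject treated under that lettering

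*Combined protocol and SAP*

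**What the plan says.** Section 10, Blinding procedures, has the compounding pharmacy allocate the letters A to E at random to the five products, vehicle included. It continues that, when the products are delivered, "a list specifying the compounds corresponding to allocated letters is supplied to the PI". Section 28, Labeling, repeats the arrangement. Neither place describes a sealed list, restricted access, an independent holder, or a code specific to a subject.

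Section 10 describes who is blind in two ways. The procedural overview says without exception: "The subject and investigator will be blinded to the identities of the treatments". The Blinding procedures paragraph is narrower: "The investigators responsible for the data collection, i.e. application, sensory tests, itch provocations, and data entry, will be blinded to the substance being applied".

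On breaking the code, the same paragraph says: "In case of serious adverse effects, the PI will breach the blinding". In all other cases unblinding waits until the primary analysis is done. No code break limited to one subject is described.

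Section 12 makes the PI responsible for monitoring compliance, data quality and safety, and Section 19 has the PI oversee all duties. The paragraph on the PI in Section 19 ends by saying that a person, whose name is removed, "will assist with recruitment, study procedures, and assess adverse events".

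**The concern.** There are two separate weaknesses.

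**Custody.** The person who oversees the trial holds the full key from the day the products arrive. That person's blind depends only on not reading a list already in hand. If the PI also takes part in study procedures or adverse event assessment, an assessor has access to the key.

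**Code structure.** A letter stands for a product, so whatever is learned about a letter in one subject applies to the next subject under the same lettering. An emergency look-up for one subject also identifies that product in subjects who have finished but have not yet been analysed.

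What is at stake is the contrast between KeAmLi and vehicle on itch AUC. The outcome is a subjective VAS rating. The stimulus depends on the operator: Section 10 has the spicules rubbed in for 30 to 45 seconds until the itch is substantial. Staff who have guessed a letter could, without meaning to, influence the stimulus or the subject's expectation. They also score local reactions on the 0 to 4 scale.

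**Working it through.** The protocol gives no figure to reproduce here. The check compares its statements and then counts how much one disclosure reveals.

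**Custody**
- Key delivered to the PI with the products: Section 10 (Blinding procedures) and Section 28 (Labeling).
- Investigator blinded, no exception: Section 10, procedural overview.
- Data-collecting investigators blinded: Section 10, Blinding procedures.
- Planned unblinding after the primary analysis: Section 10, Blinding procedures.

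The second and fourth statements agree with the first only if the PI is outside the blinded group, or holds the list without consulting it. The protocol says neither.

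**Whether a letter can be learned before the primary outcome**

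For each product, Section 10 sets this order: local safety assessment, thermal thresholds, mechanical thresholds, baseline touch-evoked itch, then cowhage. Signs of activity are therefore seen before the itch stimulus is given. For lidocaine, Section 14 says: "Common side effects include local blanching and erythema". Lidocaine is in two of the five products. The Blinding procedures paragraph groups application, sensory tests, itch provocation and data entry under the data-collecting investigators, so the same staff may see the signs and then apply the spicules.

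**How much one disclosure reveals**

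Inputs: 36 completers (Sections 6 and 12), 5 products per subject (Section 10), 30-day expiry (Section 28), 6 months of enrollment (Section 8).

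- Total applications in completers: 36 × 5 = 180.
- Subject-specific codes: one break reveals 5 of 180 = 2.8%.
- Letters never changed: the full list reveals 180 of 180. A single letter identifies 36 of 180 applications (20%) and cuts the possible assignments of products to letters from 5! = 120 to 4! = 24. What is seen in the first subject can carry forward to 36 − 1 = 35 others.
- Letters redrawn at each delivery (an assumption): 180 days / 30 = 6 batches, or 183 / 30 = 6.1, rounded up to 7. Subjects per batch are 36 / 6 = 6, or 36 / 7 = 5.1. One list then reveals about 5 × 5 = 25 to 6 × 5 = 30 applications, or 14% to 17% of 180. Carry-forward falls to about 4 or 5 later subjects.

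The batch figures assume even enrollment and continuous supply. They also place each subject within one batch; with visits up to 7 days apart, some subjects would straddle two.

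**The case against.** **A reader might infer that the investigator blind is broken from the start.** The documents do not support that. The Blinding procedures paragraph keeps the data collectors blind, and it has the PI break the code only for serious adverse effects. This implies that the list is not to be used before then. Nothing says the PI reads or shares it. The objection stands: the gap is a missing safeguard, not a demonstrated unblinding.

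**A reader might also infer that each product keeps one letter for the whole study.** No section says so. The 30-day expiry means repeat deliveries, and re-lettering is neither stated nor excluded. The 180 applications are therefore a worst case.

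**The PI's hands-on role is uncertain.** The sentence in Section 19 has its name removed, and a student researcher is also assigned procedures and data entry. The overlap is probable, not established.

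**Stopping rules limit the harm of an emergency look-up.** Section 12 stops the study for a severe adverse event, and Section 14 stops it for an allergic reaction, so few later subjects might be affected. Ratings already entered by subjects on the electronic scroll bar cannot be changed by a later break. This stands in part. The code-break trigger is worded as serious and the stopping trigger as severe. These are different terms and the sections must be reconciled. Data already collected would in any case be unblinded before analysis.

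**Skin and sensory signs do not identify a product with certainty.** Blanching or erythema points at most to a pair, lidocaine or KeAmLi. Each subject receives all five products, so within-subject contrasts give hints under any coding. This also stands. Subject-specific codes prevent carry-over between subjects, not guessing within one.

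**Conclusion.** The point holds in this form: the PI's blind is unprotected from delivery, and product-level coding lets one break, or one recognised letter, carry over to every subject under the same lettering. Opening the list reveals between about 25 to 30 applications (letters redrawn per batch) and all 180 (letters never changed), against 5 with subject-specific codes. Which end applies depends on a re-lettering rule that the protocol does not state.

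The documents do not show that the assessors are unblinded, and the size of any bias in itch AUC cannot be computed from them. The change should be made because the outcome is subjective, the present arrangement conflicts with the unqualified promise of a blinded investigator, and the remedy is cheap. It is not evidence that the trial's result would be invalid.

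**What to change.** - Keep the master list at the compounding pharmacy, or with another named person outside data collection and analysis. Revise Section 10 (Blinding procedures) and Section 28 (Labeling) to match.
- Replace the five product letters with subject-specific label codes: a fresh permutation per subject, or 180 numbered units for the 36 completers plus units for replacements.
- Supply sealed single-subject code breaks for emergencies, and log each opening.
- Release the key only after the primary analysis. Subject-specific codes cannot be grouped without a link, so after the data are locked the list holder should give the analyst a file that sorts the units into five groups under neutral names. The file can mark which two groups form the primary contrast without saying which is vehicle.
- Reconcile the two statements in Section 10 on who is blinded, and state whether the PI takes part in assessments or analysis.
- If product letters are kept, state whether they are redrawn at each delivery.

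The cost is more labels and envelopes from the pharmacy, and a slightly slower emergency look-up if the envelopes are not held on site. No extra subjects or procedures are needed.
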